9.1.1 Publication of results

The results should be made public within 24 months of the end of data collection. If a report is planned to be published in a peer-reviewed journal, then that initial release may be an abstract that meets the requirements of the International Committee of Medical Journal Editors. A full report of the outcomes should be made public no later than three (3) years after the end of data collection. Outside institutions planning publications must send copies of any intended communication in advance of publication (at least fifteen working days for presentational materials and abstracts and thirty working days for manuscripts). Principal Investigation/Institution shall have the final authority to determine the scope and content of the publications.

9.1.3 Discontinuation of study

Novartis reserves the right to discontinue any study under the conditions specified in the clinical trial agreement.

9.2 Ethics and Good Clinical Practice

This study must be carried out in compliance with the protocol and the principles of Good Clinical Practice, as described in Novartis standard operating procedures and:

ICH Harmonized Tripartite Guidelines for Good Clinical Practice 1996. Directive 91/507/EEC, The Rules Governing Medicinal Products in the European Community.

US 21 Code of Federal Regulations dealing with clinical studies (including parts 50 and 56 concerning informed consent and IRB regulations).

Declaration of Helsinki and amendments, concerning medical research in humans (Recommendations Guiding Physicians in Biomedical Research Involving Human Subjects).

The investigator agrees to adhere to the instructions and procedures described in it and thereby to adhere to the principles of Good Clinical Practice that it conforms to.

9.2.1 Institutional Review Board/Independent Ethics Committee

Before implementing this study, the protocol, the proposed informed consent form and other information to subjects, must be reviewed by a properly constituted Institutional Review Board/Independent Ethics Committee/Research Ethics Board (IRB/IEC/REB). A signed and dated statement that the protocol and informed consent have been approved by the IRB/IEC/REB must be given to Novartis before study initiation. Any amendments to the protocol, other than administrative ones, must be reviewed by Novartis approved by this committee.

9.2.2 Informed consent

The investigator must explain to each subject (or legally authorized representative) the nature of the study, its purpose, the procedures involved, the expected duration, the potential risks and benefits involved and any discomfort it may entail. Each subject must be informed that participation in the study is voluntary and that he/she may withdraw from the study at any time and that withdrawal of consent will not affect his/her subsequent medical treatment or relationship with the treating physician.

This informed consent should be given by means of a standard written statement, written in non-technical language. The subject should read and consider the statement before signing and dating it, and should be given a copy of the signed document. If the subject cannot read or sign the documents, oral presentation may be made or signature given by the subject's legally appointed representative, if witnessed by a person not involved in the study, mentioning that the patient could not read or sign the documents. No patient can enter the study before his/her informed consent has been obtained.

The informed consent form is considered to be part of the protocol, and must be submitted by the investigator with it for IRB/IEC/REB approval.

9.2.3 Declaration of Helsinki

The investigator must conduct the trial in accordance with the principles of the Declaration of Helsinki. Copies of the Declaration of Helsinki and amendments will be provided upon request or can be accessed via the website of the World Medical Association at http://www.wma.net/e/policy/17-c_e.html.

Summary of Major Changes, Protocol Amendment Dated January 28th, 2014

Protocol Section	Change
Study Objectives	The secondary endpoint of overall survival will now be collected for 5 years from study entry, updated from 1 year.
Visit Schedule and Assessments	Footnote #5 describes the imaging schedule. The schedule is unchanged; this update is to add clarity to how the imaging schedule

	changes after subjects have been on trial for >24 months.
Treatment Period Procedures	
This section now describes all study procedures rather than just those occurring throughout the first 24 months on trial.
 
Procedures for subjects on trial for >24 months were previously located in the “End of Treatment Period Procedures” section

Adverse Events	Protocol now reflects that all serious events are reported to the sponsor, regardless of whether their relatedness to study drug.
Throughout the Protocol	Minor administrative changes

Appendix A

Modified RECIST criteria (adapted from Therasse et al ³⁴).

RECIST: Response Evaluation Criteria in Solid Tumors

Eligibility: To be eligible, subjects must have at least one uni-dimensionally measurable lesion.

Measurable lesion: To be considered measurable, lesions must be equal or greater than 20mm in at least one dimension using conventional techniques (CT or MRI scan) or 10 – 16mm with spiral CT scan.

Lesions identified on physical exam and clinically measured by the investigator will automatically be considered non-target lesions. Lesion in a radiation therapy port will not be considered target lesions.

Non-measurable lesions

Non-measurable lesions are all other lesions including small lesions⁹ longest diameter less than 20mm with conventional techniques or equal or more than 10-16mm with spiral CT scan. Other examples of non-measurable lesions include bone lesions, leptomeningeal disease, ascites, pleural/pericardial effusion, lymphangitis cutis/pulmonis, cystic lesions and also abdominal masses that are not confirmed and followed by imaging techniques. Additionally, the following will be considered non-measurable for this study: Non-measurable skin lesions, peritoneal carcinomatosis, military lesions, irradiated lesions and groups of lesions that are small and numerous.

Method

All measurements should be taken and recorded in metric notation, using a ruler or calipers. All baseline evaluations should be performed as closely as possible to the beginning of treatment and never more than 4 weeks before the beginning of the treatment. The same method of assessment and the same technique should be used to characterize each identified and reported lesion at baseline and during follow-up evaluations.

Conventional CT and MRI will be performed with contiguous cuts of 10mm or less in slice thickness and spiral CT will be performed by use of up to an 8mm contiguous reconstruction algorithm. Standard whole body bone scans will be utilized to follow the non-measurable bony lesions for progression.

Measurement of lesions on chest x-ray will not be performed. CT of the chest is required for lesion measurement.

When the primary endpoint of the study is objective response evaluation, ultrasound should not be used to measure tumor lesions that are not clinically easily accessible. It may be used as a possible alternative to clinical measurements for superficial palpable lymph nodes, subcutaneous lesions and thyroid nodules. Ultrasound might also be useful to confirm the complete disappearance of superficial lesions usually assessed by clinical examination.

Tumor markers will not be used to assess objective response for the primary study endpoint.

Baseline documentation of target and non-target lesions.

All measurable lesions up to a maximum of five lesions per organ and 10 lesions in total representative of all involved organs should be identified as target lesions and recorded and measured at baseline.

Target lesions should be selected on the basis of their size (lesions with the longest diameter) and their suitability for accurate repeated measurements (either by imaging techniques or clinically).

A sum of the longest diameter (LD) for all target lesions will be calculated and reported as the baseline sum LD. The baseline for sum LD will be used as reference by which to characterize the objective tumor.

All other lesions (or sites of disease) should be identified as non-target lesions and should also be recorded at baseline. Measurement of these lesions is not required but the presence or absence of each should be noted through follow-up evaluations.

Response criteria	Evaluation of target lesions
Complete response	Disappearance of all target lesions
Partial response	At least a 30% decrease in the sum of the LD of target lesions, taking as reference the baseline sum LD
Progressive disease (PD)	At least a 20% increase in the sum of the LD of target lesions, taking as reference the smallest sum LD recorded since the treatment started or the appearance of one or more new lesions.
Stable disease (SD)	Neither sufficient shrinkage to qualify for a partial response nor sufficient increase to qualify for progressive disease, taking as reference the smallest sum LD since the treatment started

	Evaluation of non-target lesions
Complete response	Disappearance of all non-target lesions
Incomplete response/stable disease	Persistence of one or more non-target lesion(s)
Progressive disease	Appearance of one or more new lesions and/or unequivocal progression of existing non-target lesions. A clear progression of non-target lesions only is exceptional. In such circumstances, the opinion of the investigator will prevail for the purpose of deciding whether to continue treatment. Bone scans will be utilized to follow subjects at risk for bony disease progression. Because of the difficulties in interpreting changes in the intensity or size of bone lesions on bone scans, progressive disease in bone is defined as the appearance of one or more new lesions determined by the investigator to be compatible with metastases. In questionable cases, plain radiographic films or other imaging may be performed to confirm or refute the clinical suspicion.

Evaluation of Response

Response is recorded each time a CT is performed. The smallest measurements since treatment started are taken as reference for progressive disease. In general, the subject's response assignment will depend on the achievement of both target lesions and non-target lesions.

Target lesions	Non-target lesions	New lesions	Response
CR	CR	No	CR
CR	Incomplete response/SD	No	PR
PR	Non-PD	No	PR
SD	Non-PD	No	SD
PD	Any	Yes or no	PD
Any	PD	Yes or no	PD

Any Any Yes PD

Subjects with a global deterioration of health status requiring discontinuation of treatment without objective evidence of disease progression at the time should be classified as having symptomatic deterioration. Every effort should be made to document the objective progression even after discontinuation of treatment in the long term follow-up portion of the study.

In some circumstances it may be difficult to distinguish residual disease from normal tissue. When the evaluation of complete response depends on this determination, it is recommended that the residual lesion be investigated (fine needle aspirate/biopsy) to confirm the complete response status.

Response confirmation

To be assigned a status of PR or complete response, changes in tumor measurements must be confirmed by repeat assessments that should be performed no less than 4 weeks after the criteria for response are first met.

Duration of Overall Response

The duration of overall response is measured from the time measurement criteria are met for complete response or PR (whichever status is recorded first) until the first date that recurrence or progressive disease is objectively documented, taking as reference for progressive disease the smallest measurements recorded since the treatment started.

Duration of Stable Disease

SD is measured from the start of the treatment until the criteria for disease progression are met, taking as reference the smallest measurements recorded since the treatment started.

Appendix B

Drug Diary

Appendix C

Questionnaire

Appendix D

DF/HCC Multi-center Data and Safety Monitoring Plan

Appendix E

Correlative Studies Shipping Guidelines and Submission Form

Participant Name: _____ Record #: _____ Cycle #: _____

RAD001

1.) RAD001 should be taken: _____ Participant Signature: _____ Date: ____ / ____ / ____

- 1 time every other day in the morning, at approximately the same time every day when taken
- On an empty stomach or with no more than a light fat-free meal.

- 2.) Please record each dose in the calendar below, indicating what **time** the dose was taken.
- 3.) List any noticeable side effect, reason for missed dose, or other pertinent information in the "Notes" column.
- 4.) If you vomit after taking RAD001 or miss a RAD001 dose, do not repeat or make up that dose. Take your next scheduled dose on the following day. If you do not take RAD001 within 6 hours of the scheduled time this is considered a missed dose. Please record the missed dose in your diary below.
- 5.) Please do not drink or eat grapefruit juice, pomegranate juice, star fruit, and Seville oranges while taking this medication.
- 6.) Please return this diary, all empty bottles and unused pills at the end of each cycle.

Day #	Date	Time	Dose of Drug	Notes (Side effects, reason for missed dose, etc.)
1				
2				
3				
4				
5				
6				
7				
8				
9				
10				
11				
12				
13				
14				
15				
16				
17				
18				
19				
20				
21				
22				
23				
24				
25				
26				
27				
28				
29				
30				
31				

Participant Name: _____ Record #: _____ Cycle #: _____

RAD001

1.) **RAD001 should be taken:** _____ **Participant Signature:** _____ **Date:** ____/____/____

- 1 time per day in the morning, at approximately the same time every day
- On an empty stomach or with no more than a light fat-free meal.

- 2.) Please record each dose in the calendar below, indicating what **time** the dose was taken.
- 3.) List any noticeable side effect, reason for missed dose, or other pertinent information in the “Notes” column.
- 4.) If you vomit after taking RAD001 or miss a RAD001 dose, do not repeat or make up that dose. Take your next scheduled dose on the following day. If you do not take RAD001 within 6 hours of the scheduled time this is considered a missed dose. Please record the missed dose in your diary below.
- 5.) Please do not drink or eat grapefruit juice, pomegranate juice, star fruit, and Seville oranges while taking this medication.
- 6.) Please return this diary, all empty bottles and unused pills at the end of each cycle.

Day #	Date	Time	Dose of Drug	Notes (Side effects, reason for missed dose, etc.)
1				
2				
3				
4				
5				
6				
7				
8				
9				
10				
11				
12				
13				
14				
15				
16				
17				
18				
19				
20				
21				
22				
23				
24				
25				
26				
27				
28				
29				
30				
31				

ORIGINAL

Health Questionnaire

(English version for the US)

By placing a checkmark in one box in each group below, please indicate which statements best describe your own health state today.

Mobility

- I have no problems in walking about
- I have some problems in walking about
- I am confined to bed

Self-Care

- I have no problems with self-care
- I have some problems washing or dressing myself
- I am unable to wash or dress myself

Usual Activities (e.g. work, study, housework, family or leisure activities)

- I have no problems with performing my usual activities
- I have some problems with performing my usual activities
- I am unable to perform my usual activities

Pain/Discomfort

- I have no pain or discomfort
- I have moderate pain or discomfort
- I have extreme pain or discomfort

Anxiety/Depression

[figure not shown]
- I am not anxious or depressed
- I am moderately anxious or depressed
- I am extremely anxious or depressed

To help people say how good or bad a health state is, we have drawn a scale (rather like a thermometer) on which the best state you can imagine is marked 100 and the worst state you can imagine is marked 0.

We would like you to indicate on this scale how good or bad your own health is today, in your opinion. Please do this by drawing a line from the box below to whichever point on the scale indicates how good or bad your health state is today.

**Your own
health state
today**

Best
imaginable
health state

Worst
imaginable
health state

ORIGINAL

Date: / /
(month) (day) (year)

Study Name: _____

Participant's Initials: _____

Protocol #: _____

Participant's Study #:

PI: _____

PLEASE USE A
BLACK INK PEN

M. D. Anderson Symptom Inventory - Thyroid (MDASI-Thy)

Part I. How severe are your symptoms?

People with cancer frequently have symptoms that are caused by their disease or by their treatment. We ask you to rate how severe the following symptoms have been in the last 24 hours. Please rate each of these symptoms from 0 (symptom has not been present) to 10 (the symptom was as bad as you can imagine it could be).

CORE Items	Not Present											As Bad As You Can Imagine	
	0	1	2	3	4	5	6	7	8	9	10		
1. Your pain at its WORST?													
2. Your fatigue (tiredness) at its WORST?													
3. Your nausea at its WORST?													
4. Your disturbed sleep at its WORST?													
5. Your feeling of being distressed (upset) at its WORST?													
6. Your shortness of breath at its WORST?													
7. Your problem with remembering things at its WORST?													
8. Your problem with lack of appetite at its WORST?													
9. Your feeling drowsy (sleepy) at its WORST?													
10. Your having a dry mouth at its WORST?													
11. Your feeling sad at its WORST?													
12. Your vomiting at its WORST?													
13. Your numbness or tingling at its WORST?													

Date: / /
 (month) (day) (year)

Study Name: _____

Participant's Initials: _____

Protocol #: _____

Participant's Study #:

PI: _____

PLEASE USE A
BLACK INK PEN

**THYROID-Specific
Symptoms**

	Not Present										As Bad As You Can Imagine	
	0	1	2	3	4	5	6	7	8	9	10	
14. Your hoarseness at its WORST?												
15. Your problem with feeling hot at its WORST?												
16. Your problem with racing heartbeat at its WORST?												
17. Your problem with feeling cold at its WORST?												
18. Your difficulty swallowing at its WORST?												
19. Your diarrhea or loose stools at its WORST?												

Part II. How have your symptoms interfered with your life?

Symptoms frequently interfere with how we feel and function. How much have your symptoms interfered with the following items in the last 24 hours:

	Did not Interfere										Interfered Completely	
	0	1	2	3	4	5	6	7	8	9	10	
20. General activity?												
21. Mood?												
22. Work (including work around the house)?												
23. Relations with other people?												
24. Walking?												
25. Enjoyment of life?												

DFCI IRB Protocol #: 09-049

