3.2.3 Interruption or discontinuation of treatment

For patients who are unable to tolerate the protocol-specified dosing schedule, dose adjustments are permitted in order to keep the patient on study drug. Patients may be re-escalated back to the previous dose if he/she is stable, his/her symptoms are related to disease and not treatment, and you receive the PI's permission. If administration of RAD001 must be interrupted because of unacceptable toxicity, drug dosing will be interrupted or modified according to rules described in Table 3-1. Toxicity will be assessed using the NIH-NCI Common Terminology Criteria for Adverse Events, version 3.0 (CTCAEv3.0, (<http://ctep.cancer.gov/forms/CTCAEv3.pdf>)).

Table 3.0 RAD001 dose level modification guidelines

Dose level	Dose and schedule
0 (starting dose)	10 mg po daily
-1	5 mg po daily
-2	5 mg po every other day

If patients are unable to tolerate dose level -2, the patient will come off study.

Table 3-1 Criteria for dose-modification in case of suspected RAD001 toxicity and re-initiation of RAD001 treatment

Toxicity	Actions
Non-hematological toxicity	
Grade 2 (except pneumonitis – refer to Table 3-2a)	If the toxicity is tolerable to the patient, maintain the same dose. If the toxicity is intolerable to patient, interrupt RAD001 until recovery to grade ≤ 1 . Then reintroduce RAD001 at same dose. If event returns to grade 2, then interrupt RAD001 until recovery to grade ≤ 1 . Then reintroduce RAD001 at the lower dose level.
Grade 3 (except hyperlipidemia*) (except pneumonitis – refer to Table 3-2a)	Interrupt RAD001 until recovery to grade ≤ 1 . Then reintroduce RAD001 at the lower dose level. For pneumonitis consider the use of a short course of corticosteroids.
Grade 4 (except hyperlipidemia*)	Discontinue RAD001.
Hematological toxicity	
Grade 2 Thrombocytopenia (platelets $<75, \geq 50 \times 10^9/L$)	Interrupt RAD001 until recovery to grade ≤ 1 ($>75 \times 10^9/L$). Then reintroduce RAD001 at initial dose. If thrombocytopenia again returns to grade 2, interrupt RAD001 until recovery to grade ≤ 1 . Then reintroduce RAD001 at the lower dose level.
Grade 3 Thrombocytopenia (platelets $<50, \geq 25 \times 10^9/L$)	Interrupt RAD001 until recovery to grade ≤ 1 (platelets $\geq 75 \times 10^9/L$). Then resume RAD001 at one dose level lower. If grade 3 thrombocytopenia recurs, discontinue RAD001.
Grade 4 Thrombocytopenia (platelets $< 25 \times 10^9/L$)	Discontinue RAD001.

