3.3 Treatments

3.3.1 RAD001 Administration

The study drug RAD001 will be self-administered (by the patients themselves). The investigator will instruct the patient to take the study drug exactly as specified in the protocol. RAD001 will be administered orally as once daily dose of *10 mg (one 10mg tablet or two 5mg tablets)* continuously from study day 1 until progression of disease or unacceptable toxicity. Patients will be instructed to take RAD001 in the morning, at the same time each day.

RAD001 should be taken by the patient in a fasting state or with no more than a light fat-free meal. Dietary habits around the time of RAD001 intake should be as consistent as possible

Version 12

Updated: 1/28/2014

throughout the study. Tablets should be swallowed whole with a glass of water. The tablets must not be chewed or crushed and grapefruit or citrus juices should be avoided. For patients unable to swallow tablets, everolimus tablet (s) should be dispersed completely in a glass of water (containing approximately 30mL) by gently stirring, immediately prior to drinking. The glass should be rinsed with the same volume of water and the rinse should be completely swallowed to ensure that the entire dose is administered.

A dose of RAD001 is considered missed if the patient did not take RAD001 within 6 hours of the scheduled time. If vomiting occurs, no attempt should be made to replace the vomited dose. All dosages prescribed and dispensed to the patient and all dose changes during the study must be recorded.

Medication labels will comply with US legal requirements and be printed in English. They will supply no information about the patient. The storage conditions for study drug will be described on the medication label. RAD001 will be provided by Novartis. RAD001 is formulated as tablets for oral administration of 5mg and 10 mg strength. Tablets are blister-packed under aluminum foil, which should be opened only at the time of administration as drug is both hygroscopic and light-sensitive. Patients will be given a two-months supply.

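### The every-other-day drug diary tells patients who miss or vomit a dose to take the next one on what is an off day

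*Combined protocol and SAP*

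**What the plan says.** Section 3.2.3, Table 3.0, sets three dose levels: 10 mg daily, 5 mg daily and, at level -2, "5 mg po every other day". Level -2 is the only alternate-day schedule. It is also the last step: "If patients are unable to tolerate dose level -2, the patient will come off study".

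Appendix B (Drug Diary; in the combined file the pages follow the appendix title sheets) has one page for each schedule. The daily page is headed "1 time per day in the morning, at approximately the same time every day". The alternate-day page is headed "1 time every other day in the morning, at approximately the same time every day when taken".

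Item 4 reads the same on both pages. It begins "If you vomit after taking RAD001 or miss a RAD001 dose, do not repeat or make up that dose" and continues "Take your next scheduled dose on the following day".

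Section 3.3.1 adds, for the protocol as a whole, "If vomiting occurs, no attempt should be made to replace the vomited dose". It defines a missed dose by a 6-hour limit but does not say when the next dose is due.

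**The concern.** Item 4 suits daily dosing and appears to have been carried over to the alternate-day page without adaptation. On that page its last four words name a day on which no dose is due.

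Patients act on this text alone at home. The drug is self-administered from a two-month supply (Section 3.3.1), and clinic visits are every 4 weeks (Table 3.4a). The diary grid numbers the days 1 to 31 and does not mark off days. The page serves patients at the lowest permitted dose, for whom the longer interval is the only difference from level -1. A patient who follows the words literally takes an unplanned 5 mg on an off day. After a vomited dose, that puts two intakes 24 hours apart instead of 48.

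**Working it through.** The plan states no figure for this point, so the check is a comparison of texts followed by a day count.

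**Texts side by side.** Let *d* be the day of the missed or vomited dose.

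| Source | Day it implies for the next dose |
|---|---|
| Heading of the alternate-day page | *d*+2 |
| Table 3.0, level -2 | *d*+2 |
| Item 4, first sentence (no repeat, no make-up) | not *d*+1, since a tablet then would act as a make-up for a missed dose |
| Section 3.3.1 (vomited dose not replaced) | no day named, but against an extra intake |
| Item 4, second sentence, last four words | *d*+1 |

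Only the last row points to *d*+1. On the daily page *d*+1 is correct, so the same sentence causes no conflict there.

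**Day count.** Inputs: 5 mg per dose and a 48-hour interval (Table 3.0). Day 1 is the affected day. The window is 28 days, the cycle length in footnote 3 to Table 3.4a. Total mg = number of intakes × 5.

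| Case | Dosing days | Intakes | Total |
|---|---|---|---|
| Plan | 1, 3, …, 27 | 14 | 70 mg |
| Vomited, literal, schedule then shifted | 1, 2, 4, …, 28 | 15 | 75 mg |
| Vomited, literal, then back to original days | 1, 2, 3, 5, …, 27 | 15 | 75 mg |
| Missed, literal, schedule then shifted | 2, 4, …, 28 | 14 | 70 mg |
| Missed, literal, then back to original days | 2, 3, 5, …, 27 | 14 | 70 mg |
| Missed, next dose on *d*+2 | 3, 5, …, 27 | 13 | 65 mg |

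- **Vomited dose:** 75/70 = 1.07, about 7% more than planned if the vomited tablet was absorbed. If it was not, 14 × 5 = 70 mg, equal to plan.
- **Missed dose:** the literal reading gives 70 mg against 65 mg under the no-make-up rule. That is one make-up dose, but no excess over the planned 70 mg.

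**Sensitivity to the window.** Over the 31 rows printed in the diary, the plan is days 1, 3, …, 31 = 16 intakes. After a vomited dose, the shifted schedule (1, 2, 4, …, 30) also gives 16, so there is no excess. Returning to the original days gives 16 + 1 = 17. The 7% therefore belongs to one event in a 28-day window.

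**The case against.** The strongest reply is that the sentence contradicts itself and does not plainly order an extra dose. It speaks of the next *scheduled* dose, which on this page is *d*+2, and the heading and the preceding sentence agree. A careful patient might work that out. This is fair, and it limits the charge to a conflict within the instruction. It does not make the instruction right: a patient has to disregard the only explicit timing given.

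The reply can also say that the effect is small and conditional. That stands. The worst case per event is one extra 5 mg dose. The 75 mg total is well below the 5 × 28 = 140 mg at level -1 and the 10 × 28 = 280 mg at the starting dose, and the count depends on the window, as shown above. Patients at level -2 have, however, already been reduced from those doses.

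Two smaller points also stand. Not every level -2 patient need be there for intolerance, because hepatitis B reactivation without symptoms also calls for a one-level reduction (Section 3.2.6.4, Table 3-3). There are also partial safeguards: the investigator instructs the patient (Section 3.3.1), drug use and returns are recorded (Section 3.3.4), and visits are every 4 weeks. These make a repeated error less likely but do not correct the page.

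**Conclusion.** The concern holds. Item 4 of the alternate-day diary is wrong as written for the only patients who use that page, and no other text in the protocol supplies the correct day.

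The consequence is minor: at most one unplanned 5 mg intake per event, with the interval cut from 48 to 24 hours after a vomited dose. This assumes that the patient follows the literal words. Any excess of drug further assumes that the vomited tablet was absorbed. The documents give no expected number of patients at level -2 and no rate of missed or vomited doses there, so the number of events cannot be estimated.

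Nothing here affects the primary endpoint, the two-stage decision rule, the error rates or the analysis. It is a small patient-safety correction that is worth making because it is so easy to make.

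**What to change.** On the every-other-day diary page only, replace the second sentence of item 4 with: *Take your next dose on your next scheduled dosing day (do not take a dose on an off day).* Leave the daily page as it is.

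The new wording agrees with the page heading, Table 3.0, the no-make-up rule and Section 3.3.1. The cost is one sentence on one handout, IRB approval of the revised page (Section 4 requires approval before changes are implemented) and reissue to sites. Design, sample size and analysis stay as they are.
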